10.1.2.2. Laboratory data

Missing laboratory results (including immunological data) will not be replaced.

10.1.2.3. Daily recording of solicited adverse events

For the collection of solicited adverse events, a solicited adverse event will be considered present only when a daily recording of grade 1 or more is present.

10.1.2.4. Unsolicited adverse events

Unsolicited adverse event summaries are including serious adverse events unless specified otherwise.

Missing severity, relationship with study vaccine, and outcome of unsolicited adverse events will not be replaced and will appear as 'UNKNOWN' in all statistical output.

10.1.3. Data derivation**10.1.3.1. Age at vaccination in days**

When age at vaccination is to be displayed in days, it will be calculated as:

Age = date of vaccination minus date of birth

10.1.3.2. Age at vaccination in months

When age at vaccination is to be displayed in months, it will be calculated as the number of complete calendar months between the date of birth (DOB) and the date of vaccination. For example:

DOB = 10JUN2017, Date of vaccination = 09JUL2018 -> Age = 12 months

DOB = 10JUN2017, Date of vaccination = 10JUL2018 -> Age = 13 months

10.1.3.3. Age at vaccination in years

When age at vaccination is to be displayed in years, it will be calculated as the number of complete calendar years between the date of birth and the date of vaccination. For example:

DOB = 10SEP1983, Date of vaccination = 09SEP2018 -> Age = 34 years

DOB = 10SEP1983, Date of vaccination = 10SEP2018 -> Age = 35 years

10.1.3.4. Weight

Weight will be presented in kilograms. Weights reported in pounds will be converted as follows:

Weight in kilograms = Weight in pounds / 2.2

10.1.3.5. Height

Height will be presented in centimeters. Heights reported in feet and inches will be converted as follows:

Height in centimeters = Height in inches x 2.54

10.1.3.6. Body mass index (BMI)

BMI will be calculated as follows:

$$\text{BMI} = (\text{Weight in kilograms}) / (\text{Height in meters})^2$$

10.1.3.7. Temperature

Temperatures will be presented in degrees Celsius (°C). Temperatures reported in degrees Fahrenheit (°F) will be converted as follows:

$$\text{Temperature (Celsius)} = ((\text{Temperature (Fahrenheit)} - 32) \times 5)/9$$

10.1.3.8. Numerical serology results

Numerical serology results will be derived from the content of IS.ISORRES in the SDTM dataset. For assays with a specific cut-off, the following derivation rules apply:

IS.ISORRES	Derived value
“NEG”, “-”, or “(−)”	cut-off/2
“POS”, “+”, or “(+)”	cut-off
“< value” and value is <= assay cut-off	cut-off/2
“< value” and value is > assay cut-off	value
“> value” and value is < assay cut-off	cut-off/2
“> value” and value is >= assay cut-off	value
“value” and value is < cut-off	cut-off/2
“value” and value is >= cut-off	value
All other cases	missing

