5.4.2. Additional considerations

For each and all *N. meningitidis* serogroup B test strain (M14459, M07-0241084, 96217 and NZ98/254) and each of the serogroups A, C, W and Y, the percentage of subjects with hSBA titers \geq lower limit of quantitation (LLOQ) and the corresponding exact two-sided 95% CIs based on Clopper-Pearson method will be calculated [Clopper, 1934] for each study group at baseline and at one month after the 1st vaccination and at one month after the 2nd vaccination, for serogroup B test strains, and at one month after (study) vaccination of MenACWY, for serogroups A, C, W and Y.

The hSBA titers/ELISA concentrations at each blood draw visit for each study group will be logarithmically transformed (base10) to fulfil the normal distribution assumption. For each *N. meningitidis* serogroup B test strain (M14459, M07-0241084, 96217 and NZ98/254) and each of the serogroups A, C, W and Y, the GMTs/GMCs and GMRs (compared to baseline) will be calculated, with their associated two-sided 95% CIs, by

exponentiating the corresponding log-transformed means and within-subject mean difference, respectively and their 95% CIs.

The ratio of GMTs between the Group MenB+MenACWY versus Group MenB at one month after the first and the second vaccination, and the corresponding CI will be constructed by exponentiating the mean difference and the confidence limits in log10 (titer), using ANOVA with study centre included as an independent variable.

The ratio of GMTs/GMCs between the Group MenB+MenACWY versus Group MenACWY at one month after the (study) vaccination of MenACWY, and the corresponding CI will be constructed the same way, by exponentiating the mean difference and the confidence limits in log10 (titer/concentration), using ANOVA with study centre included as an independent variable.

Summary tables will show adjusted GMTs/GMCs and adjusted ratios of GMTs/GMCs for each vaccine group. To incorporate possible baseline imbalance among the vaccine groups, an analysis of covariance (ANCOVA) might be performed that incorporate baseline titers/concentrations along with study group and center as factors in the model.

The following SAS code will be used for the ANOVA model:

```
PROC GLM data = dataset;
  class trt center;
  model Ab_post = trt center;
  lsmeans trt / stderr cl tdiff pdiff;
  estimate 'Group A vs. Group B' trt 1 -1;
run;
```

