where Ab_post represents the log-transformed antibody value of the immunogenicity variable at a given post baseline timepoint, trt indicates the vaccine group, and center the site.

The following SAS code will be used for the ANCOVA model:

```
PROC GLM data = dataset;
  class trt center Ab_pre;
  model Ab_post = trt center Ab_pre;
  lsmeans trt / stderr cl tdiff pdiff;
  estimate 'Group A vs. Group B' trt 1 -1;
run;
```

where Ab_post represents the log-transformed antibody value of the immunogenicity variable at a given post baseline timepoint, trt indicates the vaccine group, center the site, and Ab_pre the log-transformed antibody baseline value of the immunogenicity variable.

If the statistical model does not converge due to the factor “centre”, merging some centres or including instead “country” in the model will be considered.

For each *N. meningitidis* serogroup B test strain (M14459, M07-0241084, 96217 and NZ98/254) and each of the serogroups A, C, W and Y, the percentages of subjects with fourfold increase in hSBA titers, and the corresponding exact two-sided 95% CIs based on the Clopper-Pearson method [[Clopper, 1934](#)] against these strains will be calculated

for each study group at one month after the 1st vaccination and one month after the 2nd vaccination, for serogroup B test strains, and at one month after (study) vaccination of MenACWY, for serogroups A, C, W and Y. The CIs for the rate difference between groups will be constructed using the method of Miettinen and Nurminen [[Miettinen](#), 1985].

The percentage of subjects with fourfold increase in hSBA titers one month after the 1st and one month after the 2nd vaccination, for serogroup B test strains, and one month after (study) vaccination, for serogroups A, C, W and Y, relative to baseline is defined as:

- If the baseline titer is <limit of detection (LOD), then post-vaccination titer should be ≥ 4 x LOD or \geq LLOQ, whichever is greater
- If the baseline titer is \geq LOD but <LLOQ, then post-vaccination titer should be ≥ 4 x LLOQ
- If the baseline titer is \geq LLOQ, then post-vaccination titer should be ≥ 4 x the baseline titer

Summary tables will show unadjusted percentages and unadjusted “between-group” differences.

The following table contains the LOD and LLOQ values to be used.

Table 5 LOD, LLOQ and ULOQ values

Serogroups / B strains	LOD*	LLOQ*	ULOQ*
A	5	12	4295
C	4	8	54828
W	4	8	10057
Y	4	10	7624
M14459	4	5	Not defined
96217	6	14	Not defined

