10.1.3.9. Geometric mean titres (GMTs) and concentrations (GMCs)

Geometric Mean Titre (GMT) or Concentration (GMC) calculations are performed by taking the inverse logarithm of the mean of the log titre or concentration transformations. Antibody titres or concentrations below the cut-off of the assay will be given an arbitrary value of half the cut-off of the assay for the purpose of GMT/GMC calculation. The cut-off value is defined by the laboratory before the analysis and is described in the protocol.

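### A serology result reported as below x, with x above the assay cut-off, is analysed as x, so an upper bound is treated as a measured titre and can be scored as at or above the LLOQ

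*SAP*

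**What the plan says.** SAP 10.1.3.8 opens with "For assays with a specific cut-off, the following derivation rules apply". Three of its rows matter here:

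- Reported as less than a value, "and value is <= assay cut-off": derived as half the cut-off.
- Reported as less than a value, "and value is > assay cut-off": derived as the value.
- Reported as a plain value, "and value is >= cut-off": derived as the value.

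SAP 10.1.3.9 adds: "Antibody titres or concentrations below the cut-off of the assay will be given an arbitrary value of half the cut-off". That covers only results below the cut-off, so it leaves the second row unchanged. SAP 9.1 and 9.2, where a study-specific derivation would stand, are both marked not applicable.

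On what the cut-off is, SAP 10.1.3.9 says: "The cut-off value is defined by the laboratory before the analysis and is described in the protocol". Protocol Table 13 gives both an LOD and an LLOQ for each hSBA, and its footnote on assay cut-offs is attached to both columns. SAP 5.4.2 introduces its own Table 5 with "The following table contains the LOD and LLOQ values to be used" and again lists both limits.

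The endpoints that use these derived values include the percentage of subjects at or above the "lower limit of quantitation (LLOQ) and the corresponding exact two-sided 95% CIs based on Clopper-Pearson method will be calculated" (SAP 5.4.2), the fourfold increase, and the GMTs, GMCs and GMRs.

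**The concern.** A result reported as `<x` says that the titre is below x. The second row assigns it x, the lowest value that the result excludes, and makes it indistinguishable from a sample measured at x. The row above it treats a censored result in the opposite way, by halving.

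The consequence is clearest for the binary secondary endpoints. A sample known only to be below some limit can be counted as quantifiable or as a fourfold responder. For geometric means the rule pushes the value upward. At baseline it lowers the fold rise and can raise the fourfold threshold. The baseline table that splits subjects at the LLOQ (SAP 5.1.1) is affected in the same way.

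**Working it through.** The plan states no figure that depends on this row, so there is none to reproduce. The check applies the row to the limits in SAP Table 5. It covers hSBA only, because Protocol Table 13 leaves the IgG limits to be determined.

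**Step 1: `<LLOQ` under each reading of cut-off.** The last column is the fourfold threshold for a baseline below LOD, the greater of 4 × LOD and LLOQ.

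| Assay | LOD | LLOQ | `<LLOQ` derived, cut-off = LOD | `<LLOQ` derived, cut-off = LLOQ | Fourfold threshold |
|---|---|---|---|---|---|
| A | 5 | 12 | 12 | 6 | 20 |
| C | 4 | 8 | 8 | 4 | 16 |
| W | 4 | 8 | 8 | 4 | 16 |
| Y | 4 | 10 | 10 | 5 | 16 |
| M14459 | 4 | 5 | 5 | 2.5 | 16 |
| 96217 | 6 | 14 | 14 | 7 | 24 |
| NZ strain | 4 | 6 | 6 | 3 | 16 |
| M13520 | 4 | 6 | 6 | 3 | 16 |

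The LLOQ exceeds the LOD in every row. With cut-off = LOD, `<LLOQ` therefore always becomes the LLOQ and is scored as at or above it, although the result says the opposite. With cut-off = LLOQ it becomes LLOQ/2 and is scored correctly. With the Protocol Table 13 limits, only M07-0241084 (LOD = LLOQ = 4) escapes under cut-off = LOD.

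**Step 2: `<x` with x above the LLOQ.** Under either reading the derived value is x and counts as at or above the LLOQ. The true titre may lie on either side, so the classification is unsupported.

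**Step 3: fourfold increase, baseline below LOD.**

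- Serogroup C `<16` becomes 16 and meets the threshold of 16, although a titre below 16 cannot reach 16.
- Serogroup A `<24` becomes 24 and passes 20, and 96217 `<28` becomes 28 and passes 24. Here the true titre could be on either side.

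**Step 4: baseline.** Take 96217 with cut-off = LOD and a baseline reported as `<14`. It is derived as 14, so the fourfold threshold is 4 × 14 = 56. If the true baseline was below LOD, the threshold should have been 24. If it lay between LOD and LLOQ, the threshold is 4 × LLOQ = 56 either way.

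**Step 5: size.** Let f be the share of a group reported as `<LLOQ` under cut-off = LOD. The documents do not give f, so 1%, 5% and 10% are assumptions. With 250 evaluable subjects per group (Protocol 10.1), the percentage at or above LLOQ rises by 100 × f points. The GMT is multiplied by (LLOQ / replacement)^f.

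| f | Subjects of 250 | Points added | GMT factor vs LLOQ/2 (2^f) | GMT factor vs LOD/2, serogroup A ((12/2.5)^f) |
|---|---|---|---|---|
| 1% | 2.5 | 1 | 1.007 | 1.016 |
| 5% | 12.5 | 5 | 1.035 | 1.082 |
| 10% | 25 | 10 | 1.072 | 1.170 |

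**Step 6: primary comparison.** Against LLOQ/2, the between-group GMT ratio is multiplied by 2^(f in the concomitant group − f in the comparator). Equal shares give 2^0 = 1, no shift. A share of 5% in one group and none in the other gives 2^0.05 = 1.035.

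**The case against.** The strongest reply is that the row may never be used. The documents do not describe how the laboratory reports low results, and the fourfold definition has its own class for baselines between LOD and LLOQ. That suggests numeric reporting in that band, in which case `<LLOQ` would not arise. This is a fair inference, and it limits the point. It does not settle it, because the reporting format is nowhere stated. There is also a sign the other way. With cut-off = LLOQ, the derived LLOQ/2 is at or above the LOD for A (6 against 5), C and W (4 against 4), Y (5 against 4) and 96217 (7 against 6). Derived values could then not identify baselines below LOD for those assays.

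Two stronger readings are tempting:

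- **The rule misclassifies against the LLOQ whichever limit is the cut-off.** It does not. With cut-off = LLOQ, `<LLOQ` is correct, and larger upper bounds are unsupported rather than always wrong.
- **The rule favours non-inferiority.** At Visit 2 the concomitant group's sample serves eight hSBAs plus IgG, against four plus IgG in Group MenACWY (Protocol Table 14). A reader might infer that short volume forces higher starting dilutions, and so more `<x` results, in that group. The protocol's stated response to short volume is priority ranking of assays. No section describes raised dilutions, and the laboratory is blinded to treatment (Protocol 7.3).

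An objection to the remedy also stands in part. Excluding undeterminable results may remove mostly low titres and so raise the percentage at or above LLOQ.

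**Conclusion.** The point holds as a defect in a stated derivation rule. Misclassification against the LLOQ is certain if two conditions hold together: the cut-off is the LOD, and the laboratory reports `<LLOQ`. It then affects all eight rows of SAP Table 5. If the cut-off is the LLOQ, the remaining problem is `<x` with x above the LLOQ, which is counted as quantifiable without support and can be scored as a fourfold response.

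The effect falls on the percentage at or above LLOQ, the fourfold increase, and within-group GMTs and GMRs. The documents give no ground for claiming bias in the primary GMT ratio, which moves only if such results are more frequent in one group. Their number is not in the documents and may be zero. The point is worth correcting because the rule is wrong where it applies and the correction is small.

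**What to change.** 1. State in SAP 10.1.3.8 whether the cut-off is the LOD or the LLOQ for each assay.
2. Replace the row so that `<value` is never analysed as the value. For GMT, GMC and GMR use half the reported limit, and not less than half the cut-off. When the value exceeds the cut-off, half of it always does.
3. Classify the binary endpoints from the reported result, not from the halved number. This is needed because `<16` halves to 8, which equals the LLOQ for serogroups C and W.
   - Value at or below LLOQ: class as below LLOQ.
   - Value above LLOQ: do not count it as at or above LLOQ, or as a fourfold responder, on the upper bound alone. Treat it as not determinable. One case is determinable: for the fourfold endpoint, a reported limit no higher than the applicable threshold is a known non-response.
4. Add a sensitivity analysis that counts the undeterminable results as below LLOQ.

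The cost is one derivation row, one classification rule and one sensitivity table. A few results may become not determinable. Leaving them out can itself raise the percentage slightly, which the sensitivity analysis would show. Halving can also give a derived value below the cut-off that differs from half the cut-off (with cut-off 6, `<8` becomes 4 rather than 3), a minor inconsistency to accept. If no such results occur, nothing changes.

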5. STUDY DESIGN

5.1. Scientific rationale for study design

The purpose of this study is to demonstrate the non-inferiority of the antibody response in terms of Human Serum Bactericidal Assay (hSBA) using human complement GMTs against *N. meningitidis* test strains indicative of serogroups A, C, W, Y, and B, after concomitant rMenB+OMV NZ and MenACWY vaccine administration to either vaccine alone in healthy subjects 16-18 years of age.

The selection of the study population is based on ACIP recommendations for use of meningococcal vaccines [ACIP, 2011]. Routine administration of a MenACWY vaccine for all persons aged 11 through 18 years is recommended. A single dose of vaccine should be administered at 11 or 12 years of age, and a booster dose should be administered at 16 years of age. Adolescents who receive their first dose at 13 through 15 years of age should receive a booster dose at 16 through 18 years of age. In Europe, *Menveo* has been approved by EMA for active immunization of children (from 2 years of age), adolescents and adults at risk of exposure to *N. meningitidis* groups A, C, W and Y,

to prevent invasive disease. The use of this vaccine should be in accordance with official recommendations.

To be eligible for this study design, all subjects must have received a previous vaccination with a quadrivalent meningococcal conjugate vaccine (MenACWY; *Menveo* or *Menactra*) at least 4 years prior to study start. The available data support interchangeability of the 2 licensed meningococcal conjugate vaccines [ACIP, 2013]. Consequently, a booster dose of *Menveo* can be administered, regardless of the vaccine brand used for the previous dose.

[figure not shown]
Data collected from this study may support the concomitant use of rMenB+OMV NZ and MenACWY in healthy subjects 16-18 years of age.

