10.1.2. Sample size calculation

For the immune response to rMenB+OMV NZ, sample size calculations are based on hSBA titer data from the GSK V102_03 and V72_41 studies and for the immune response to MenACWY, data from GSK V59P13E1 study and V102_02 study (ELISA GMCs) is used.

Sample size/power calculations are based on specific fixed values for the

- non-inferiority margin,
- standard deviations of (the distributions of) the logarithmically transformed (base of 10) hSBA titers for the strains M14459, 96217, NZ98/254 and M07-0241084.
- standard deviations of (the distributions of) the logarithmically transformed (base of 10) hSBA titers for the serogroups A, C, W and Y,
- ratios of the GMTs medians of (the distribution of) the hSBA titers for strains M14459, 96217, NZ98/254 and M07-0241084 when rMenB+OMV NZ is administered with MenACWY versus when rMenB+OMV NZ is administered alone (one ratio per strain),
- ratios of the GMTs/GMCs of (the distribution of) the hSBA titers for the serogroups A, C, W and Y when MenACWY is administered with rMenB+OMV NZ vs when MenACWY is administered alone (one ratio per serogroup).

Standard Deviations for hSBA Titer:

In [Table 19](#) the standard deviations are listed that were used in the power calculation, along with the 80% upper limit of the confidence interval (CI) for standard deviation.

For the primary objective 1, hypothesis 1, testing of rMenB+OMV NZ when given concomitantly with MenACWY to rMenB+OMV NZ given alone, test of treatment Group MenB+MenACWY versus treatment Group MenB, the standard deviations from studies V102_03 and V72_41 were used.

For the primary objective 2, hypothesis 2, testing of MenACWY when given concomitantly with rMenB+OMV NZ to MenACWY given alone, test of treatment Group MenB+MenACWY versus treatment Group MenACWY, the standard deviations from study V59P13E1 GrIV_V were used.

For the secondary objective, hypothesis 3, testing of MenACWY when given concomitantly with rMenB+OMV NZ to MenACWY given alone based on ELISA GMCs, test of treatment Group MenB+MenACWY versus treatment Group MenACWY, the standard deviations from study V102_02 were used.

Table 19 Observed SDs with the Upper Limits of the Two-Sided 80% CI for the Logarithmically (base of 10) Transformed hSBA Titers

Hypothesis	study	strain	sd	N	alpha	df	Est_sd
1	V102_03	M14459	0.65413	92	0.2	91	0.72443
1	V72_41	96217	0.25408	30	0.2	29	0.30774
1	V102_03	NZ98/254	0.56100	92	0.2	91	0.62129

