1	V102_03	M07-0241084	0.55235	92	0.2	91	0.61171
2	V59P13E1GrIV_V	MenA	0.46542	119	0.2	118	0.50866
2	V59P13E1GrIV_V	MenC	0.54356	117	0.2	116	0.59455
2	V59P13E1GrIV_V	MenW	0.57507	118	0.2	117	0.62875
2	V59P13E1GrIV_V	MenY	0.59519	118	0.2	117	0.65075
3	V102_02	MenA	0.67891	59	0.2	58	0.77338
3	V102_02	MenC	0.56615	59	0.2	58	0.64493
3	V102_02	MenW	0.50023	57	0.2	56	0.57128
3	V102_02	MenY	0.53432	58	0.2	57	0.60943

The testing of the hypotheses will be done simultaneously on all the strains and serogroups.

Power Calculation and Sample Size Results of the Non-inferiority Testing of rMenB+OMV NZ, First Primary Objective, Referred to as Hypothesis 1

In [Table 20](#) the results are presented of the power calculation (in %) with T1 MenB strains M14459, 96217, NZ98/254 and M07-0241084 with sample size raising from 200 to 300 per treatment group. The individual power calculations are presented along with the power for all serogroup B strains. The power for rMenB+OMV NZ is the multiplication of the power for all 4 individual strains. A non-inferiority margin of 0.5 and a GMT ratio between treatments of 0.9 was used.

Table 20 Power (in %) for the Individual and for the Overall MenB Strains

Hypothesis	N	Power M14459	Power 96217	Power NZ98_254	Power M07_0241084	Power MenB
1	200	94.01	100	98.38	98.62	91.21
1	210	94.98	100	98.75	98.95	92.80
1	220	95.80	100	99.04	99.20	94.11
1	230	96.49	100	99.26	99.39	95.19
1	240	97.08	100	99.43	99.54	96.08
1	250	97.57	100	99.57	99.65	96.81
1	260	97.98	100	99.67	99.74	97.40
1	270	98.33	100	99.75	99.80	97.89
1	280	98.62	100	99.81	99.85	98.28
1	290	98.86	100	99.86	99.89	98.60
1	300	99.06	100	99.89	99.92	98.87

Power Calculation and Sample Size Results of the Non-inferiority Testing of MenACWY, Second Primary Objective, Referred to as Hypothesis 2

In [Table 21](#) the results are presented of the power calculation (in %) with MenACWY with sample size raising from 200 to 300 per treatment group. The individual power calculations are presented along with the power for all MenACWY serogroups combined. The power for MenACWY is the multiplication of the power of all 4 individual

serogroups. A non-inferiority margin of 0.5 and a GMT ratio between treatments of 0.9 was used.

Table 21 Power (in %) for the Individual Serogroups and for the Overall MenACWY Serogroups

Hypothesis	N	Power MenA	Power MenC	Power MenW	Power MenY	Power MenACWY
2	200	99.88	98.99	98.17	97.46	94.60
2	210	99.92	99.24	98.58	97.98	95.79
2	220	99.95	99.43	98.90	98.40	96.72

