In summary to have an overall power of 90% or more, the minimum sample size need to be N=250 subjects per group. To account for a 20% drop out rate, N=315 subjects per group need to be enrolled. For the study, with 3 treatment groups, N=945 subjects need to be enrolled to have 750 eligible subjects.

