6. ANALYSIS INTERPRETATION

The primary objective is divided in three primary endpoints. The first one regards safety and will be only descriptive. The two other endpoints will be achieved if non-inferiority is demonstrated. Non-inferiority is demonstrated if for each of the four serogroups A, C, W and Y (the four serogroup B test strains: M14459, 96217, NZ98/254 and M07-0241084), the lower limit of the 2-sided 95% confidence interval of the between-group ratio of hSBA GMTs is >0.5 for group MenB+MenACWY versus group MenACWY (for group MenB+MenACWY versus group MenB).

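### MenACWY hSBA results reported only as above the ULOQ would be analysed as the ULOQ, which favours non-inferiority if co-administration lowers titres; the SAP should define their handling and add a censored-data sensitivity analysis

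*SAP*

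**What the plan says.** SAP 10.1.3.8 lists the derivation rules for serology results. One row covers a result reported as greater than a value "and value is >= assay cut-off"; the derived number is that value. A separate row keeps a plain numeric result at or above the cut-off unchanged. The cut-off in this table is the assay's lower cut-off, and the section does not mention the ULOQ.

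The ULOQs are in SAP 5.4.2, under "Table 5 LOD, LLOQ and ULOQ values": A 4295, C 54828, W 10057, Y 7624, and not defined for the B strains. The sentence introducing that table reads "The following table contains the LOD and LLOQ values to be used", so no use is assigned to the ULOQ column. SAP 10.1.3.9 discusses substitution only below the cut-off, and SAP 9.1 and 9.2, where study-specific derivations and methods would go, are marked not applicable.

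SAP 5.4.2 then fits an ANOVA with group and centre to the log10 titres. SAP 6 declares non-inferiority if, for each serogroup, "the lower limit of the 2-sided 95% confidence interval of the between-group ratio of hSBA GMTs is >0.5".

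**The concern.** Replacing a right-censored result by the limit removes more from the arm with the higher titres. If the combined arm is truly lower, the estimated ratio is pulled toward 1 and the variance is understated. In a superiority test the loss of contrast would be conservative; in a non-inferiority test both effects work in favour of the claim. If the combined arm were truly higher, the ratio would instead be pulled down toward 1.

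Four of the eight co-primary comparisons are exposed: hSBA A, C, W and Y at Visit 2. The MenB comparisons are not, because no ULOQ is defined for those strains. Protocol 5.1 requires that "all subjects must have received a previous vaccination with a quadrivalent meningococcal conjugate vaccine", so the Visit 2 samples follow a repeat dose. High titres are therefore conceivable, but the documents give no MenACWY GMTs and no expected share above the ULOQ. The plan neither shows that such results will be rare nor provides an analysis in case they are not.

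**Working it through.** **Inputs.** Margin and planned ratio, Protocol 10.1.2: "A non-inferiority margin of 0.5 and a GMT ratio between treatments of 0.9 was used". SDs of log10 titre from Protocol Table 19, column Est_sd, which gives the observed SDs "along with the 80% upper limit of the confidence interval (CI) for standard deviation": A 0.50866, C 0.59455, W 0.62875, Y 0.65075. Size, Protocol 10.1.2: "the minimum sample size need to be N=250 subjects per group". ULOQs from SAP Table 5. Log10 titres normal (SAP 6.1). One-sided 2.5% per serogroup, from the lower limit of a two-sided 95% CI.

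**Reproducing the plan's figure.** Two-sample t-test with shift log10(0.9/0.5) = 0.2553, SE = SD × √(2/250), 498 degrees of freedom. Power is A 99.99%, C 99.77%, W 99.49%, Y 99.22%; the product is 98.47%, as in Protocol Table 21.

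**Effect of substitution.** Let U = log10(ULOQ) and let p be the assumed share of the MenACWY-alone arm above the ULOQ. Then:

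- control mean μC = U − SD × z(1−p); combined-arm mean μT = μC + log10(0.5);
- for each arm, with a = (U − μ)/σ, the substituted mean is μΦ(a) − σφ(a) + U(1 − Φ(a));
- the substituted second moment is (μ² + σ²)Φ(a) − σ(U + μ)φ(a) + U²(1 − Φ(a));
- the false non-inferiority rate is the probability that the lower 95% limit exceeds log10(0.5).

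*Example, serogroup A, p = 10%.* U = log10(4295) = 3.633, so μC = 3.633 − 1.2816 × 0.50866 = 2.981 (GMT 957) and μT = 2.680. After substitution the control arm has mean 2.9570 and SD 0.4654; the combined arm has mean 2.6740 and SD 0.4950. The difference is −0.2830, a ratio of 0.521 instead of 0.50. SE = √((0.4654² + 0.4950²)/250) = 0.0430, against 0.0455 without substitution. The noncentrality is (−0.2830 + 0.3010)/0.0430 = 0.42, which gives a rate of 6.2%.

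**All four serogroups, true ratio 0.5:**

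| Control share above ULOQ (assumed) | Expected observed ratio | False non-inferiority rate per serogroup |
|---|---|---|
| 0% | 0.500 | 2.5% |
| 1% | 0.502 | 2.7% |
| 2% | 0.504 | 2.9% |
| 5% | 0.510-0.511 | 3.7-3.8% |
| 10% | 0.521-0.524 | 5.6-6.2% |
| 20% | 0.548-0.552 | 13-16% |

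Simulation (40,000 trials per setting, run at 0, 1, 5, 10 and 20%) agrees. In a smaller check for serogroup A at 20% (600 runs), substitution gave 15.8% and a censored-normal likelihood gave 2.3%.

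**As a shift in the margin.** With 10% above the ULOQ, the pass rate at a true ratio of 0.48 is 2.6-2.9%. With 20%, the pass rate at 0.45 is 2.1-2.7%. The test then behaves roughly as if the margin were 0.48 or 0.45.

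**At the planned ratio of 0.9.** The observed ratio moves only to 0.904 with 5% and 0.909 with 10%.

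**Control GMTs these shares would need, with Est_sd.** For 5%: A 626, C 5768, W 930, Y 648. For 10%: A 957, C 9485, W 1573, Y 1117.

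The calculation ignores the centre term and substitution below the cut-off, and assumes equal SDs in the two arms.

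**The case against.** The strongest reply is that nothing may be substituted at all. The greater-than row belongs to the sponsor's standard rules, compares with the lower cut-off, and never mentions the ULOQ. No section says the laboratory will report such results as above the ULOQ; if it dilutes to an end-point, the numeric titre is kept. This stands. A reader might infer that the plan clips high titres and therefore has an inflated error rate. The documents support only the conditional statement.

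Second, the share is unknown, and a boosted population does not by itself establish a large one. This also stands. Est_sd is an upper confidence limit and widens the tail; with the observed SDs in Table 19, a 10% share would need higher control GMTs: A 1088, C 11026, W 1843, Y 1316. The SDs come from an earlier study, while Protocol Appendix 2 describes a new hSBA format here, so the mapping from GMT to share is itself uncertain.

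Third, the rates apply at a true ratio of exactly 0.5 and per serogroup, while study success needs all eight comparisons. That is correct, and the margin shift is the fairer summary. Still, if one serogroup sits at the margin and the others pass comfortably, its inflation carries through to the joint verdict.

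A reader might also conclude that a censored model should replace the ANOVA as the co-primary analysis. The documents do not justify that: whether any result exceeds the ULOQ is unknown, and the verdict would then rest on an assumed upper tail.

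**Conclusion.** The point holds as a conditional gap in the SAP. A stated substitution rule, wherever it applies to a MenACWY hSBA result above the ULOQ, biases that co-primary comparison toward success when the combined arm is truly lower. The effect is nil with numeric end-point titres, negligible at 1-2% above the ULOQ, noticeable from about 5%, and material at 10-20%, where the margin effectively slips to about 0.48 and 0.45. These figures assume log10-normal titres, the Est_sd values, 250 per arm and equal SDs. The documents supply neither the share above the ULOQ nor the reporting format, so they do not show that the error rate is actually inflated. This is an inexpensive improvement to settle before unblinding; the primary analysis need not change.

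**What to change.** Keep the pre-specified ANOVA as the primary analysis and add the following to the SAP.

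1. In 10.1.3.8, for hSBA A, C, W and Y: use a numeric end-point (re-diluted) titre where one exists; classify a result available only as above the ULOQ as right-censored at the ULOQ.
2. Tabulate the percentage of results available only as above the ULOQ, by group and serogroup.
3. If there are any such results, report beside the primary result a censored-normal maximum-likelihood sensitivity analysis of the four MenACWY hSBA GMT ratios and their 95% CIs, on log10 titre with group and centre (for example PROC LIFEREG).

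The cost is a few lines of SAP text, one table and one standard procedure. The limitation is that the sensitivity analysis relies on log-normality in the upper tail, an assumption the plan already makes.
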